Robotic-assisted surgery (RAS) represents a further step in this evolution. These systems, which use a navigated robotic arm to assist screw placement, aim to enhance accuracy and reduce variability—which may be especially beneficial for less experienced surgeons. RAS may also streamline intraoperative workflow and support minimally invasive approaches. While early results are promising, there remains limited evidence on the broader clinical benefits, especially during the early learning phase of implementation [4]. Robotic-assisted spine surgery is not sanctioned by the Swedish Association of Authorities and Regions, unless performed in clinical trials.

This study aims to evaluate the clinical introduction of robotic systems in spine surgery, focusing on their impact on reoperations, screw placement accuracy, complications, outcome, and intraoperative workflow.

7. Objectives

This study has three main objectives, analysed in three different substudies: To study screw placement accuracy, learning curve, and reoperations.

Secondary Objectives: To assess complications, patient-reported outcomes, length of stay, surgical time, and cost-effectiveness.

8. Trial Design

Multicenter, non-randomized observational cohort study with consecutive patient inclusion.

9. Study Setting

All hospitals in Sweden performing spinal surgery will participate.

10. Eligibility Criteria

Inclusion Criteria:

- Treatment with pedicle screws in the cervical, thoracic, lumbar spine and/or sacrum.
- All ages and spinal diagnoses

Exclusion Criteria:

- Treatment without pedicle screws

Consent

-All patients will be treated according to each hospital's routine. Patient consent will therefore not be needed.

11. Interventions

Experimental Group: Robotic-assisted pedicle screw insertion using available equipment. Currently available systems are Brainlab Cirq and Mazor Robotics, but others systems may be used.

Control Group: Patients undergoing non-robotic-assisted (freehand or navigation-assisted) pedicle screw placement.

12. Outcomes

Primary objectives and outcomes

Substudy 1 primary outcome - Screw placement accuracy (binary per-patient outcome)

- Proportion of patients in which at least one screw is not accurately placed.

Substudy 2 primary outcome- Learning curve (surgical time)

-To evaluate when time in surgery is no longer decreasing in robotic-assisted surgery.

Substudy 3 primary outcome - Reoperation rate at 2 years

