Assuming a minimum of 4 screws per patient, the estimated probability of at least one non-clinically acceptable screw is 12% in the robotic group and 25% in the navigated and free hand group.

Using a two-sided alpha of 0.05, 80% power, and a 1:6 group ratio, the required sample size is 71 patients in the robotic-assisted surgery group and 426 patients in the non-robotic-assisted surgery group, for a total of 497 patients. We added patients to 75 in the robotic-assisted surgery group, for a total of 501 patients, to be able to include an equal number of patients from Örebro, Umeå and Uppsala. This estimate is conservative, as most patients are expected to receive more than 4 screws, which would increase the likelihood of detecting placement differences.

The primary analysis will use either mixed-effects logistic regression or logistic regression with cluster-robust standard errors to account for intra-patient correlation of screw outcomes.

A secondary analysis of robot-assisted surgeries after the first 501 patients may be performed.

Substudy 2 - Primary outcome - Learning curve (surgical time)

To evaluate the learning curve associated with robotic-assisted surgery, we will model operative time as a function of case number. Operative time is expected to decrease with experience, then plateau. We will use mixed-effects piece-wise linear regression with the surgeon as a random effect to estimate the case number at which operative time levels off. We will look both at wheel-in wheel-out time (primary), and skin-to-skin time (secondary). We expect to do this analysis after each center has performed 100 robot-assisted spine surgeries, in total 300 surgeries.

We have not conducted a traditional power analysis for this substudy, as the objective is not to test a binary hypothesis but to estimate when operative time stabilizes. If no clear inflection point is observed, this will be interpreted as evidence that the learning curve is either very short (already completed), very gradual, or inconsistent. Such a result would itself be informative, and will require us to compare operative times with today's standard of care, navigated or free hand surgery.

Substudy 3- Primary outcome – Reoperation rate at 2 years

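### Substudy 2 commits to reading a missing inflection point at 300 cases as evidence about the learning curve, and leaves out imprecision as an explanation

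*Protocol*

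**What the plan says.** The learning curve is one of three main objectives (protocol section 7). Section 12 states its primary outcome as "To evaluate when time in surgery is no longer decreasing in robotic-assisted surgery".

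Section 14, Substudy 2, gives the design:

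- Expected shape: "Operative time is expected to decrease with experience, then plateau".
- Model: "We will use mixed-effects piece-wise linear regression with the surgeon as a random effect to estimate the case number at which operative time levels off".
- Endpoint: "We will look both at wheel-in wheel-out time (primary), and skin-to-skin time (secondary").
- Timing and size: "We expect to do this analysis after each center has performed 100 robot-assisted spine surgeries, in total 300 surgeries".
- Power: "We have not conducted a traditional power analysis for this substudy". The reason given is that the aim is estimation and not a test.

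The same section then settles how a null result will be read: "If no clear inflection point is observed, this will be interpreted as evidence that the learning curve is either very short". A gradual curve and an inconsistent curve are the other readings offered. The section regards such a result as informative and says it will lead to a comparison of operative times with navigated or freehand surgery.

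**The concern.** The three readings all describe the curve, and none describes the data. A breakpoint can also go unseen because 300 cases of mixed surgery are too few or too variable to show it. The rule gives that possibility no place, so absence of evidence is counted as evidence.

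Giving up a power calculation because the aim is estimation does not help. An estimate needs enough precision to carry the conclusion drawn from it, and section 14 states no precision for 300 cases.

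If the rule is followed as written, noise can be reported as a finding on a main objective: a real learning period could be described as already over, or as slow, when the data could not tell. Section 6 says robotic spine surgery is currently sanctioned in Sweden only within clinical trials, so the conclusion may influence adoption.

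**Working it through.** **1. The rule on its face.** Each reading needs its own positive evidence.

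- Very short curve: an interval for the total change in time that excludes a meaningful fall.
- Gradual curve: a slope whose interval stays below zero over the observed range.
- Inconsistent curve: visible variation between surgeons in slope or breakpoint.
- Imprecision: wide intervals that are compatible with all of the above.

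Failure to see an inflection can occur under all four, so by itself it favours none of them. Comparing robotic times with standard care shows whether robotic surgery is slower or faster overall. It does not separate the four.

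**2. The plan's own figure.** 3 centres × 100 = 300 cases. This reproduces. There is no power or precision figure to reproduce.

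**3. Illustration, with assumed inputs.** The protocol supplies the 300 cases, the three centres, the piecewise model and the surgeon effect. Everything else is assumed: 2, 3 or 4 surgeons per centre, case number counted within surgeon, a linear fall of 30 to 60 minutes and then a flat line, and a residual SD of 50 to 75 minutes.

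Model: time = surgeon effect + b1·x + b2·max(x − k, 0) + error, where x is the surgeon's case number and k the breakpoint. Surgeon means are removed by within-surgeon centring, which approximates a random intercept. An inflection counts as detected if the best-fitting k beats a straight line at 5%, with the critical value simulated under a straight line.

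- Cases per surgeon: 300/6 = 50, 300/9 ≈ 33, 300/12 = 25.
- Cases left after a plateau at surgeon case 15: 35, about 18, and 10.
- Size of the fall: from 30/75 = 0.4 SD to 60/50 = 1.2 SD.

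Result for a plateau at case 15: detected in about 12% to 95% of trials. For a plateau at case 25 with two surgeons per centre (25 cases left after it): 13% to 78%. The ends of these ranges move by a few points with the exact form of the test.

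**4. The same question in SD units.** A separate simulation used 2,000 trials per scenario and 300 cases over 3, 6 or 12 surgeons. The true plateau lay at case 15–50, 10–30 or 8–12 respectively, so every scenario contains data after it.

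| Total fall / residual SD | Detected | Missed |
|---|---|---|
| 0.50 | 12–26% | 74–88% |
| 0.75 | 24–52% | 48–76% |
| 1.00 | 38–81% | 19–62% |
| 1.33 | 63–96% | 4–37% |

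Letting slopes differ between surgeons changed little. With 6 surgeons and a plateau at case 20, detection was 24% instead of 23% at 0.5 SD, and 67% instead of 70% at 1.0 SD.

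**5. Precision of the breakpoint.** This is the quantity the substudy sets out to estimate. With 3 surgeons (100 cases each) and a true plateau at case 30, the median 95% interval is about 76 cases wide at 0.5 SD and 29 cases wide at 1.0 SD. The first covers most of a 100-case curve.

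**6. Scale.** In that same setting, 300 cases give about 80% detection at a fall of 1.0 SD. Information grows roughly as N × (fall/SD)², so a fall of 0.5 SD would need about 300 × (1.0/0.5)² = 1,200 cases.

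**The case against.** Several points on the other side are sound.

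- **The percentages rest on assumptions.** A reader might infer that a real plateau would usually be missed, or that imprecision is the most likely reason for a null result. The documents support neither. They give no SD, fall, plateau location or surgeon count, and section 14 does not say whether case number is counted per surgeon. With a large fall and an early plateau, detection reaches 91% to 96%.
- **Some scenarios must not be counted.** With four surgeons per centre each has 25 cases, so a plateau at case 25 leaves nothing after it. The straight line is then the true model, and the 4% to 7% detection is just the 5% error rate. Such cells are no evidence of missed plateaus and are left out above.
- **Adjustment may reduce the noise.** Section 20 lists diagnosis, number of levels and number of screws among its adjustment variables. If the SDs above are before adjustment, the residual SD becomes SD × √(1 − R²). To turn a fall of 0.5 SD into 1.0 SD, adjustment must explain R² = 1 − 0.5² = 75% of the within-surgeon variance. Detection would then still be only 38% to 81%.
- **The protocol does not commit to a completed curve.** It offers three readings and a follow-up comparison. This softens the consequence, but all three are still statements about the curve.
- **Detail may sit in the SAP.** A criterion for a clear inflection, and routine reporting of intervals, are ordinary SAP content, and their absence here is no finding. The interpretation rule is different, because the protocol states it.

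A reader might also infer that the substudy should wait for all robotic cases. The protocol does not support that as the primary analysis. Figure 2 places the learning curve in 2026–2028 with inclusion running to 2029, and sections 11 and 15 allow further systems and hospitals to join, which would change the population.

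**Conclusion.** The concern holds as a fault in the stated interpretation rule. That part needs no simulation: section 14 treats a missing inflection as evidence about the curve, omits a plausible fourth explanation, and has no precision figure behind 300 cases.

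How much this matters depends on quantities the documents do not give. Under the assumed inputs with a plateau at surgeon case 15, detection runs from about 12% to 95%. It is low when the fall is near half a residual SD and high when it exceeds one SD and few surgeons share the cases. The protocol has not shown that its own setting is at the favourable end. This should be corrected. It does not invalidate the substudy, and it does not show that 300 cases is the wrong number.

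**What to change.** Replace the interpretation sentence in section 14, Substudy 2, with wording such as:

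> If no inflection is detected, the result is reported as inconclusive unless the 95% confidence interval for the change in operative time (or for the slopes) excludes a fall of [stated] minutes. Conclusions about the shape of the curve rest on the 95% confidence intervals for the breakpoint and for both slopes.

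The investigators need to state the meaningful fall before the data are analysed. The comparison with standard care can stay, but not as a way of choosing among the explanations.

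Keep the 300-case analysis as primary. Optionally add a supplementary refit on the further robotic cases collected for Substudy 3. That substudy needs 420 or 866 robotic patients, and the planned 7,200 patients at 1:6 imply about 7,200/7 ≈ 1,029. Such a refit should be labelled supplementary because centres and systems may differ.

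Cost: one sentence of protocol text, a little extra analysis and no additional patients. The real downside is that some results will be labelled inconclusive.

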The primary outcome is the occurrence of reoperations of any cause within 2 years from the index surgery. The expected reoperation rate in the non-robotic group is likely to be higher than 3-5% over a 2-year period [9–11], and may in the robotic-assisted group be 1% or less [12]. A difference of 2 percentage points or greater is considered clinically meaningful. Power analyses (80% power, α 0.05) have been made in two scenarios, with reoperation rates of 3% vs 1%, or 5% vs 3%. We estimate a ratio of 1:6 for robotic-assisted surgery vs navigation-assisted or free hand surgeries.

Comparing 3% and 1% reoperation rates, 420 robotic-assisted surgery patients and 2,520 non-robotic surgery patients are needed (yielding a total sample size of 2,940 patients). In case reoperation rates are 5% and 3%, 866 robotic-assisted surgery patients and 5,196 non-robotic surgery patients are needed (yielding a total sample size of 6,062 patients). An increased proportion of robotic-assisted surgeries or a larger difference in reoperation rates will decrease the total sample size.

An estimated 1800 patients per year are treated with pedicle screw instrumentation at the hospitals, totaling 7,200 patients in 4 years. If we after 4 years deem that the sample size will not be reached in a reasonable time frame, the study will be stopped.

No patients will be lost to follow-up, as outcomes will be ascertained through linkage with national quality, health and surgical registries, requiring no active participation from patients or clinical teams beyond standard registration. If a patient moves abroad before the 2-year period has come to an end, their existing data will be used.

To reduce confounding by indication in this non-randomized design, we will apply both propensity score matching (PSM) and inverse probability weighting (IPW). The propensity score will be estimated using logistic regression, incorporating relevant baseline covariates including age, sex, BMI, smoking status, diagnosis, number of levels fused, revision status, surgical approach (minimally invasive vs. open), interbody device use, and fixed effects for hospital site.

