In the primary analysis, 1:2 nearest-neighbor matching without replacement will be used, with a caliper of 0.2 standard deviations of the logit of the propensity score. Covariate balance after matching will be evaluated using standardized mean differences (SMDs), with $SMD < 0.1$ considered acceptable. Outcome analysis will be performed using Cox proportional hazards regression with robust standard errors to account for matched pairs.

As a secondary analysis, IPW will be used to create a pseudo-population in which treatment assignment is independent of observed covariates. Stabilized weights will be applied, and outcome analysis will be conducted using weighted regression models, adjusted for baseline covariates to enhance robustness.

Although both methods are suitable for dealing with moderate imbalances in group size, it is important to note that reducing the size of the non-robotic group may limit the number of matches available during PSM and could increase variance in the IPW analysis if extreme weights arise. These risks will be mitigated through careful diagnostics, including evaluation of match yield, standardized mean differences, and weight distributions. Overlap weighting or trimming will be considered if weight instability is detected.

While the study is powered at 80% based on the reduced cohort, adjusted analyses using propensity score methods may yield a slightly reduced effective sample size due to matching inefficiency or variance inflation. However, both approaches are expected to preserve sufficient power to detect the prespecified effect size, given the projected event rate and available sample size.

Multiple imputation will be used to handle missing baseline data, and all patients will be included in the final analysis. An increased proportion of robotic surgeries relative to non-robotic surgeries will decrease the overall sample size requirement to detect the same effect.

Secondary outcome - Screw placement precision

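### Substudy 3: the 80% power at 420 and 866 robotic patients belongs to an unmatched 1:6 comparison; under the planned 1:2 matched Cox analysis it is about 60% and 67%

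*Protocol*

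**What the plan says.** Protocol section 14, Substudy 3, takes two scenarios for any-cause reoperation within 2 years (non-robotic vs robotic): 3% vs 1% and 5% vs 3%, with 80% power and α 0.05. On allocation it says: "We estimate a ratio of 1:6 for robotic-assisted surgery vs navigation-assisted or free hand surgeries". For the first scenario, "420 robotic-assisted surgery patients and 2,520 non-robotic surgery patients are needed"; for the second, "866 robotic-assisted surgery patients and 5,196 non-robotic surgery patients are needed". No formula or test is named.

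The same section then fixes the primary analysis as 1:2 nearest-neighbour matching without replacement, with a caliper. After that, "Outcome analysis will be performed using Cox proportional hazards regression with robust standard errors", to allow for the matched pairs. Inverse probability weighting is secondary. The section closes by saying that the study has 80% power, that propensity methods may lower the effective sample size a little, and that both are expected to leave enough power.

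**The concern.** The sizes are worked out for one comparison and the primary analysis is another. The sizing uses six controls per robotic patient; the analysis keeps at most two. The sizing formula is also not one that follows a Wald test when events are few, and at a 1% rate only 420 × 0.01 = 4.2 robotic reoperations are expected.

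This is the outcome that the study timeline labels the main study. The protocol also ties a decision to stop after 4 years to whether the sample size can be reached. If 2,940 patients were taken as sufficient, a real fall from 3% to 1% would be missed about four times in ten in the primary analysis, and a null result could be misread.

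**Working it through.** **Inputs (Protocol section 14).** Rates 1% vs 3% and 3% vs 5%; α 0.05; power 80%; ratio 1:6; 1:2 matching; Cox with robust standard errors. Sidedness is not stated for Substudy 3. I take it as two-sided, as in Substudy 1 ("Using a two-sided alpha of 0.05, 80% power, and a 1:6 group ratio"). Loss to follow-up is taken as zero, as the protocol says: "No patients will be lost to follow-up, as outcomes will be ascertained through linkage with national quality, health and surgical registries".

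**1. Reproduce the plan's sizes.** Arcsine formula, with h = 2·arcsin√p2 − 2·arcsin√p1 and k controls per robotic patient:

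n(robotic) = (1 + 1/k) × ((1.960 + 0.842)/h)²

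- 3% vs 1%: h = 0.1478; (7/6) × 359.15 = 419.0, rounded up to 420.
- 5% vs 3%: h = 0.1029; (7/6) × 741.8 = 865.5, rounded up to 866.

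Both match exactly, and this was the only variant tried that did. The two-sided pooled chi-square formula gives 498 and 933.

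**2. Power at the stated sizes, all controls kept (1:6).** Expected events (robotic and control) are 4.2 and 75.6 in the first scenario, 26.0 and 259.8 in the second. The first four rows are exact binomial enumerations; the last simulates Cox regression (exponential times, censoring at 2 years, no covariates, 4,000 and 6,000 replicates).

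| Test | 420:2,520, 3% vs 1% | 866:5,196, 5% vs 3% |
|---|---|---|
| Likelihood ratio | 79.8% | 79.6% |
| Score | 73.0% | 77.3% |
| Wald, log odds ratio | 67.9% | 76.6% |
| Wald, log hazard ratio | 67.8% | 76.6% |
| Cox, robust standard error | 68% | 77% |

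**3. Power in the planned 1:2 set, every robotic patient matched.** Expected events are 4.2 and 25.2 (420:840), and 26.0 and 86.6 (866:1,732).

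| Method | 420:840 | 866:1,732 |
|---|---|---|
| Arcsine formula | 69.6% | 69.6% |
| Pooled formula | 61.9% | 66.8% |
| Exact Wald (log hazard ratio; log odds ratio) | 59%; 60% | 67%; 67% |
| Simulated Cox, robust standard error | 60% | 68% |

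The arcsine entries follow from Φ(h·√(n·k/(1 + k)) − 1.960). In the first scenario n·k/(1 + k) falls from 420 × 6/7 = 360 to 420 × 2/3 = 280, a loss of 22%: Φ(0.1478 × √280 − 1.960) = Φ(0.514) = 0.696.

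**4. At the forecast size.** 7,200/7 is about 1,029 robotic patients at 1:6. Exact Wald power is:

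- 3% vs 1%: 99% unmatched, 97% matched 1:2.
- 5% vs 3%: 84% unmatched, 75% matched 1:2.

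**The case against.** **The stated sizes are valid.** This stands. Arcsine is a standard method, and the totals and the 1:6 ratio agree. A reader might infer that 420 and 866 are arithmetic errors; they are not.

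**80% is not peculiar to the arcsine formula.** This also stands. A reader might infer that no other method reaches 80% at these sizes. The exact likelihood-ratio test has about 80% in both scenarios, and the unpooled z formula gives 92% and 86%. But neither is the planned test. Schoenfeld's formula gives 93% and 87%, yet it is too optimistic with so few robotic events: the simulated Cox score test reaches only 73% and 78%.

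**The protocol does not name a Wald test.** True. It names Cox regression with robust standard errors, and a Wald-type test is the natural reading. The matched shortfall does not depend on that reading, since the arcsine formula itself falls to about 70% at 1:2.

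**The unmatched figures describe no planned analysis.** Agreed. They only separate the effect of the test from the effect of matching. For 5% vs 3% the test alone costs about 3 points, which is small.

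**Recruitment may run well past 420.** This limits the consequence. At 866 robotic patients, simulated Cox power for 3% vs 1% is about 97% unmatched and 93% matched. The protocol also expects control rates that may exceed its scenarios. Neither makes the statement about 420 + 2,520 true, and neither lifts 5% vs 3% to 80% in the matched set.

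**Conclusion.** The point holds as a mismatch between how Substudy 3 was sized and how it will be analysed. At the stated sizes the primary analysis has about 60% (3% vs 1%) and 67% (5% vs 3%) power, not 80%. A fall of 13 to 20 points is more than the slight loss that the protocol allows for.

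These figures assume two-sided testing, constant hazards, complete follow-up, no residual confounding, no within-match correlation, and a match for every robotic patient. Robotic patients left unmatched by the caliper would lower them. Events are rare, so the Wald figures for 3% vs 1% move by a point or so between the odds-ratio, hazard-ratio and simulated versions.

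A reader might also infer that the pooled chi-square sizes (498 with 2,988, or 933 with 5,598) would restore 80%. They would not: after 1:2 matching the exact Wald test has about 70% at both.

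**What to change.** In section 14, Substudy 3:

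- Name the formula and the sidedness behind 420 and 866, and say that they refer to an unmatched 1:6 comparison.
- Restate the power of 420 and 866 robotic patients for the 1:2 matched Cox analysis: about 60% and 67%, lower with caliper losses.
- Replace the sentences on 80% power, a slightly smaller effective sample size and sufficient power so that they agree with those figures.
- State power at the forecast of 7,200 patients as well: about 97% for 3% vs 1% and about 75% for 5% vs 3% in the matched set.

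If the sponsor wants to keep an 80% claim, the target must be computed for the 1:2 set. For 5% vs 3% that is 1,113 robotic patients by the arcsine formula (1.5 × 741.8) or 1,164 by the pooled formula, both above the roughly 1,029 forecast.

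The cost is protocol wording and a less favourable stated power. No data collection changes.

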Patients will be included consecutively at each site during the enrollment window which is planned to be four years (2025–2029). Currently robotic-assisted spine surgery is available in two hospitals (Umeå and Örebro), with a third hospital waiting for their equipment to be installed (Uppsala). If other hospitals install robotic-assisted surgery during the study period this will just result in more patients involved in the robotic-assisted arm of the trial, which would result in a potentially faster inclusion of the needed amount of patients. We still believe that during the study period more patients will be operated with non-robotic-assisted methods than with robotic-assisted methods.

16–17. Allocation and blinding

No randomization or blinding will be performed. If a planned robotic-assisted surgery is abandoned after the start of surgery, the patient will be included in the robotic-assisted group (i.e. intention to treat principle).

18. Data collection methods

Data will be collected through national registries (Swespine, the Swedish Fracture Register, the Swedish PeriOperative Register, hospital systems (electronic health records, surgical planning software, Picture Archiving and Communication System; PACS and others). PROMs will be recorded preoperatively, and at follow-ups (Swespine: 1, 2 and 5 years; the Swedish Fracture Register: 1 year). Images will be retrieved using standardized CT protocols and assessment will be made by at least two researchers independently.

19. Data management

Data will be collected and managed in compliance with GDPR. Regular validation and updates will occur every 6–12 months. Final datasets will be stored at Uppsala University for a minimum of 15 years.

20. Statistical methods

Statistical analysis will compare outcomes using appropriate parametric or non-parametric tests,

including survival methods. Baseline characteristics will be adjusted for using multivariable models. Adjustment variables include age, diagnosis, comorbidities, previous spine surgery, number of levels, number of screws, robotic system type, use of navigation or free-hand surgery and hospital.

Analysis is currently planned to be performed in R. Interim analyses will be performed when half of the patients have been included. Sensitivity analyses will be performed as described earlier.

21. Data monitoring

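### Substudy 3 gives two target sizes, 2,940 and 6,062, and does not say which governs; at the smaller one, power for 5% vs 3% is about 42–50%, not 80%

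*Protocol*

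**What the plan says.** Protocol section 14, Substudy 3, reports: "Power analyses (80% power, α 0.05) have been made in two scenarios, with reoperation rates of 3% vs 1%, or 5% vs 3" per cent. Both cases use one allocation assumption: "We estimate a ratio of 1:6 for robotic-assisted surgery vs navigation-assisted or free hand surgeries". Both have the same gap between groups, which the section sets as its threshold: "A difference of 2 percentage points or greater is considered clinically meaningful".

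- For 3% vs 1% it asks for 420 robotic-assisted and 2,520 other patients, "yielding a total sample size of 2,940 patients".
- The other case begins "In case reoperation rates are 5% and 3" per cent and asks for 866 and 5,196, in all 6,062.

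The section expects a non-robotic rate probably above 3–5% and a robotic rate of perhaps 1% or less. It forecasts 1,800 eligible patients a year, "totaling 7,200 patients in 4 years".

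Three provisions then rely on a single size:

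- The study is stopped after four years if the required number is judged out of reach (section 14).
- Power is said to be 80% for a reduced cohort that is not defined. Propensity score methods are expected to cost little of it (section 14).
- "Interim analyses will be performed when half of the patients have been included" (section 20).

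**The concern.** The two totals differ by a factor of 6,062 / 2,940 = 2.06. Section 14 does not choose between them, and its own expectations do not settle the matter. The expected robotic rate belongs to the smaller case, while the expected control rate lies at or above the 3% that the smaller case assumes.

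This has practical consequences. Robotic-assisted patients are the scarce group: section 15 lists two hospitals with the equipment and a third waiting for it. If the study has between 420 and 866 of them after four years, it has met one target and missed the other, so the stopping provision gives opposite answers. Half of the patients is 1,470 under one reading and 3,031 under the other. The 80% is true of each size only in its own scenario.

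The main risk is that 2,940 comes to be treated as sufficient while the rates are those of the second case. The study would then have about an even chance, or less, of detecting the difference it calls clinically meaningful.

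**Working it through.** **Inputs.** Rates, 80% power, α 0.05, the 1:6 ratio and accrual come from section 14, Substudy 3. Sidedness is not stated there. I take it as two-sided, as in Substudy 1: "Using a two-sided alpha of 0.05, 80% power, and a 1:6 group ratio". No loss to follow-up, as the plan assumes.

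**Step 1: reproduce the plan's sizes.** Arcsine formula:

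n(robotic) = (1.960 + 0.842)² × (1 + 1/6) / h², with h = 2·asin(√p2) − 2·asin(√p1).

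- 3% vs 1%: h = 0.1478, n = 419.01, rounded up to 420; 420 × 7 = 2,940.
- 5% vs 3%: h = 0.1029, n = 865.5, rounded up to 866; 866 × 7 = 6,062.

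Both stated totals are reproduced. Other common formulas do not give both figures: pooled two-sided gives 498 and 933, unpooled 290 and 727.

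**Step 2: power at the smaller size when the truth is 5% vs 3%.**

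Arcsine: power = Φ(h·√(n·k/(1+k)) − 1.960), where k is the number of controls per robotic patient.

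- 420:2,520: Φ(0.1029 × √360 − 1.960) = Φ(−0.008) = 49.7%.
- 866:5,196: 80.0%.

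Pooled z: power = Φ((d − 1.960·SE0)/SE1). SE0 uses the pooled rate (3 + 6 × 5)/7 = 4.71%; SE1 uses the separate rates.

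- 420:2,520: (0.0200 − 0.0219)/0.0094 = −0.20, giving 42.0%.
- 866:5,196: (0.0200 − 0.0152)/0.0065 = 0.73, giving 76.6%.

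| Size | Arcsine | Pooled z | Unpooled Wald |
|---|---|---|---|
| 420:2,520 | 49.7% | 42.0% | 56.8% |
| 866:5,196 | 80.0% | 76.6% | 86.4% |

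The Wald column is the most favourable, but its formula does not reproduce the plan's sizes.

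**Step 3: the larger size in the first scenario.** At 866:5,196 with 3% vs 1%, power is 98.1% (arcsine) or 97.8% (pooled z).

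**Step 4: feasibility.** 6,062 / 1,800 = 3.4 years. At 1:6, 7,200 patients include 7,200/7 ≈ 1,029 robotic-assisted. Reaching 866 within 7,200 needs a robotic share of 866/7,200 = 12.0%, against 1/7 = 14.3% assumed.

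**Step 5: the planned primary analysis.** Matching is 1:2, so 866 robotic patients keep at most 1,732 controls. For 5% vs 3%, with every robotic patient matched:

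- arcsine: Φ(0.1029 × √577.3 − 1.960) = Φ(0.51) = 69.5%;
- pooled z: 66.8%.

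**Step 6: can the cases be told apart without group labels?** Expected pooled rates are (1 + 6 × 3)/7 = 2.7% and (3 + 6 × 5)/7 = 4.7%. Choosing the size at their midpoint, 3.7%, gave a simulated type I error of 4.9–5.0% (400,000 runs at each common true rate from 2% to 5%).

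**The case against.** Presenting two scenarios is ordinary sensitivity work, and the design runs on time rather than on a count: consecutive inclusion over four years, with a forecast above both totals. If the forecast holds, the larger size is reached anyway. This stands, and it makes stopping at 2,940 less likely. It does not tell the reader which size the stopping provision, the interim look and the power statement refer to.

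A reader might go further and infer that the size will be picked from the group-specific reoperation rates, which would inflate the type I error. The protocol does not say so, nor that enrolment ends at 2,940.

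- Testing at 2,940 and continuing to 6,062 if not significant would give about 8.3%, and an added efficacy test at 1,470 about 11.4%. Neither rule is in the plan.
- The result depends on the rule. Stopping on an observed 2-point advantage gives 5.0–6.2%; choosing the nearer scenario from both group rates gives 4.6–5.2%.
- The timing hardly allows it. With steady accrual, patient 2,940 enters at 2,940/1,800 = 1.6 years and completes two years at 3.6, after patient 6,062 has entered at 3.4. Patient 1,470 enters at 0.8 years, before anyone has two-year follow-up.
- Group-specific rates are not needed, because the two cases share one difference and are separated by the pooled rate.

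One might also say that power is halved. By the plan's own formula it falls from 80% to 49.7%, a loss of 30 points and not half.

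**Conclusion.** The point holds as a missing designation with a measurable consequence. Substudy 3 has two targets and no statement of which governs, so three provisions lack a fixed reference. Treating 2,940 as sufficient gives about 42–50% unadjusted power for 5% vs 3%, against the stated 80%. This rests on a two-sided 5% test, an exact 1:6 ratio and no loss to follow-up; an unpooled Wald test would put it at 56.8%.

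The 80% also belongs to the unadjusted 1:6 comparison. Under 1:2 matching it is about 67–70% at best for the larger target in the 5% vs 3% case, so the expectation that matching preserves sufficient power needs qualifying. No type I error finding follows from what is written. The change is inexpensive and worth making.

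**What to change.** In section 14, name 6,062 patients, with at least 866 robotic-assisted, as the single Substudy 3 target, and keep 3% vs 1% as a sensitivity case in which power is about 98%. State the robotic minimum separately, because the 1:6 ratio is only an estimate and a total alone does not secure it. Refer the four-year stopping decision and the section 20 interim look to this target; half is then 3,031 patients.

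Reword the power statement: 80% is for the unadjusted 1:6 comparison, and about 67–70% for 1:2 matching with all 866 matched. Naming the target does not by itself restore 80% for the matched analysis.

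If both sizes are kept, state that the choice rests only on the pooled reoperation rate without group labels (about 2.7% vs 4.7% expected, cut at 3.7%). This helps less than it seems: at the forecast accrual, complete two-year data on 2,940 patients arrive only after 6,062 have been enrolled.

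The cost is a few sentences and the option of finishing at 2,940. Accrual stays within the forecast if the 1:6 ratio holds.
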